3.2 Placebo Information

- a. Placebo pellets (Nu-Pareli sugar spheres) filled into size 1 blue/blue capsugel shells
- b. Stability: Expiration after 60 months.
- c. Storage: Store at room temperature (15°C to 25°C). Do not refrigerate or freeze.

4.0 STAGING CRITERIA

Breast Cancer Staging Criteria, AJCC 7th Edition, 2009

DEFINITION OF TNM

Primary Tumor (T)

Definitions for classifying the primary tumor (T) are the same for clinical and for pathologic classification. If the measurement is made by physical examination, the examiner will use the major headings (T1, T2 or T3). If other measurements, such as mammographic or pathologic measurements are used, the subsets of T1 can be used. Tumors should be measured to the nearest 0.1 cm increment.

TX	Primary tumor cannot be assessed
T0	No evidence of primary tumor
Tis	Carcinoma in situ
Tis (DCIS)	Ductal carcinoma in situ
Tis (LCIS)	Lobular carcinoma in situ
Tis (Paget's)	Paget's disease of the nipple not associated with invasive carcinoma and/or carcinoma in situ (DCIS and/or LCIS) in the underlying breast parenchyma. Carcinomas in the breast parenchyma associated with Paget's disease are categorized based on the size and characteristics of the parenchymal disease, although the presence of Paget's disease should still be noted.
T1	Tumor 20 mm or less in greatest dimension
T1mic	Microinvasion 1 mm or less in greatest dimension
T1a	Tumor more than 1 mm but no more than 5 mm in greatest dimension
T1b	Tumor more than 5 mm but not more than 10 mm in greatest dimension
T1c	Tumor more than 10 mm but not more than 20 mm in greatest dimension
T2	Tumor more than 20 mm but not more than 50 mm in greatest dimension
T3	Tumor more than 50 mm in greatest dimension
T4	Tumor of any size with direct extension to chest wall and/or skin (ulceration or skin nodules)
T4a	Extension to chest wall, not including pectoralis muscle adherence/invasion
T4b	Ulceration and/or ipsilateral satellite nodules and/or edema (including peau d'orange) of the skin, which do not meet the criteria for inflammatory carcinoma
T4c	Both T4a and T4b
T4d	Inflammatory carcinoma

Regional Lymph Nodes (N)

Clinical

NX	Regional lymph nodes cannot be assessed (e.g., previously removed)
N0	No regional lymph node metastasis
N1	Metastasis to movable ipsilateral level I, II axillary lymph node(s)
N2	Metastasis in ipsilateral level I, II axillary lymph nodes fixed or matted, or in clinically detected* ipsilateral internal mammary nodes in the absence of clinically evident axillary lymph node metastasis
N2a	Metastasis in ipsilateral level I, II axillary lymph nodes fixed to one another (matted) or to other structures
N2b	Metastasis only in clinically detected* ipsilateral internal mammary nodes and in the absence of clinically evident level I, II axillary lymph node metastasis
N3	Metastasis in ipsilateral infraclavicular (level III axillary) lymph node(s) with or without level I, II axillary lymph node involvement, or in clinically detected* ipsilateral internal mammary lymph node(s) and in the presence of clinically evident level I, II axillary lymph node metastasis; or metastasis in ipsilateral supraclavicular lymph node(s) with or without axillary or internal mammary lymph node involvement

N3a	Metastasis in ipsilateral infraclavicular lymph node(s)
N3b	Metastasis in ipsilateral internal mammary lymph node(s) and axillary lymph node(s)
N3c	Metastasis in ipsilateral supraclavicular lymph node(s)

**Clinically detected* is defined as detected by imaging studies (excluding lymphoscintigraphy) or by clinical examination and having characteristics highly suspicious for malignancy or a presumed pathologic macrometastasis based on fine needle aspiration biopsy with cytologic examination.

Distant Metastasis (M)

M0	No clinical or radiographic evidence of distant metastasis
----	--

STAGE GROUPING

Stage IA	T1*	N0	M0
	T0	N1mi	M0
Stage IB	T1*	N1mi	M0
Stage IIA	T0	N1**	M0
	T1*	N1**	M0
	T2	N0	M0
Stage IIB	T2	N1	M0
	T3	N0	M0
Stage IIIA	T0	N2	M0
	T1*	N2	M0
	T2	N2	M0
	T3	N1	M0
	T3	N2	M0
Stage IIIB	T4	N0	M0
	T4	N1	M0
	T4	N2	M0
Stage IIIC	Any T	N3	M0

* T1 includes T1mic

** T0 and T1 tumors with nodal micrometastases only are excluded from Stage IIA and are classified Stage IB

NOTE: Stage designation may be changed if post-surgical imaging studies reveal the presence of distant metastases, provided the studies are carried out within 4 months of diagnosis in the absence of disease progression and provided that the patient has not received neoadjuvant therapy.

5.0 ELIGIBILITY CRITERIA

Each of the criteria in the following section must be met in order for a patient to be considered eligible for registration. Use the spaces provided to confirm a patient's eligibility. For each criterion requiring test results and dates, please record this information on the Onstudy Form (and submit to the Data Operations Center in Seattle (see [Section 14.0](#)). Any potential eligibility issues should be addressed to the Data Operations Center in Seattle at [name] prior to registration.

In calculating days of tests and measurements, the day a test or measurement is done is considered Day 0. Therefore, if a test is done on a Monday, the Monday 4 weeks later would be considered Day 28. This allows for efficient patient scheduling without exceeding the guidelines. **If Day 14, 28, 30, 42 or 90 falls on a weekend or holiday, the limit may be extended to the next working day.**

SWOG Patient No. _____

Patient's Initials (L, F, M) _____

5.1 Disease Related Criteria

- _____ a. Patients must be women with histologically confirmed estrogen receptor (ER) and/or progesterone receptor (PgR) positive invasive carcinoma of the breast (Stage I-III) with no evidence of metastatic disease (M0).
- _____ b. Patients must have completed mastectomy or breast sparing surgery, and must have recovered from all side effects of the surgery. If patients were treated with chemotherapy and/or radiation therapy, these treatments must be completed at least 28 days prior to study registration. Patients should have recovered from all Grade 2 or higher side effects of chemotherapy and/or radiation therapy with the exception of alopecia and peripheral neuropathy. Concurrent bisphosphonate and trastuzumab therapies are allowed.

5.2 Clinical/Laboratory Criteria

- _____ a. Patients must be post-menopausal, as defined by at least one of the following:
 - 1. ≥ 12 months since the last menstrual period OR
 - 2. prior bilateral oophorectomy OR
 - 3. previous hysterectomy with one or both ovaries left in place (or previous hysterectomy in which documentation of bilateral oophorectomy is unavailable) AND (unless ≥ 60 years of age) FSH values consistent with the institutional normal values for the post menopausal state OR
 - 4. have been on LHRH agonist therapy for at least 3 months and estradiol levels drawn within 28 days prior to registration are consistent with the institutional normal values for post-menopausal state.
- _____ b. Patients must currently be taking one of the following aromatase inhibitor (AI) doses for at least 21 days prior to registration and plans to continue for at least an additional 180 days after registration. Patients may have received any number of prior AI therapies, but the first AI therapy must have started no more than 36 months prior to registration.
 - 1. anastrozole (Arimidex®) 1 mg daily
 - 2. letrozole (Femara®) 2.5 mg daily
 - 3. exemestane (Aromasin®) 25 mg daily

SWOG Patient No. _____

Patient's Initials (L, F, M) _____

- _____ c. Patients must have aromatase inhibitor (AI) associated musculoskeletal symptoms that began or increased after starting AI therapy. New musculoskeletal pain must not be due specifically to fracture or traumatic injury.
- _____ d. Patients must have completed the **S1202** Brief Pain Inventory-Short Form (BPI-SF) within 7 days prior to registration. Patients must have an "average pain" of at least 4 on the BPI-SF (item #4).
- _____ e. Patients must have Zubrod performance status of 0-2 (see [Section 10.3](#)).
- _____ f. Patients must have no known allergy or hypersensitivity to duloxetine or any of the inactive ingredients in the matching placebo.
- _____ g. Patients must not have any contraindicated concurrent illnesses listed on the duloxetine package insert including:
- Current primary psychiatric diagnosis (schizophrenia, psychosis) or suicidal ideation, history or bipolar disorder, or seizure disorder
 - History of alcohol or other substance abuse or dependence within 365 days prior to registration.
 - Chronic liver disease
 - End stage renal disease
 - Uncontrolled narrow-angle glaucoma
 - Clinically significant coagulation disorder
- _____ h. Patients must not take MAO-Inhibitors for 14 days before registration or any time during study treatment. Concomitant therapy with heparin and warfarin is also not permitted at registration or while on protocol treatment. Aspirin is permitted (see [Section 8.2](#)).
- _____ i. Patients must have a calculated creatinine clearance > 30 mL/min. The serum creatinine value used in the calculation must have been obtained within 28 days prior to registration.
- Calculated creatinine clearance = $\frac{(140 - \text{age}) \times \text{wt (kg)} \times 0.85}{72 \times \text{creatinine (mg/dL)}}$
- _____ j. Patients must have adequate hepatic function as evidenced by all of the following within 28 days prior to registration: AST and ALT both within 3 x Upper Limit of Normal based on institutional values, and total bilirubin within the upper limit of normal based on institutional values.
- _____ k. Patients must not require selective serotonin reuptake inhibitors (SSRIs) or tricyclic antidepressants during study participation. Patients must have been able to taper and discontinue treatment with these medications at least 7 days prior to registration (28 days for fluoxetine), and must not be experiencing antidepressant withdrawal symptoms (e.g., dizziness, nausea, sleep disturbance, or other sensory disturbances). **Patients must not have previously taken the serotonin norepinephrine reuptake inhibitors (SNRI) duloxetine or milnacipran.** Prior venlafaxine is allowed as long as it was not taken for treatment of pain (eg, prior treatment for hot flashes is permitted).

SWOG Patient No. _____

Patient's Initials (L, F, M) _____

(Section 5.2k contd.)

NOTE: Patients requiring antidepressants for management of depression are not appropriate candidates for this placebo-controlled study, but those who are on antidepressants for other indications, such as hot flash management, may be able to tolerate a time off of antidepressant therapy.

- _____ l. Patients who are receiving treatment with narcotics, tramadol, gabapentin, and/or pregabalin must have been taking a stable dose for at least 30 days prior to registration.
- _____ m. Patients must be able to complete study questionnaires in English or Spanish.
- _____ n. Patients must not have concurrent medical/arthritis disease that could confound or interfere with evaluation of pain or efficacy including: inflammatory arthritis (rheumatoid arthritis, systemic lupus, spondyloarthritis, psoriatic arthritis, polymyalgia rheumatica) and cancer involving the bone. Patients with osteoarthritis are eligible.

5.3 Specimen Submission Criteria

- _____ a. Patients must be willing to submit blood samples for correlative studies as outlined in [Section 15.0](#). Baseline samples must be obtained prior to beginning protocol treatment.

5.4 Regulatory Criteria

- _____ a. All patients or their legally authorized representative must be informed of the investigational nature of this study and must sign and give written informed consent in accordance with institutional and federal guidelines.
- _____ b. As a part of the OPEN registration process (see [Section 13.3](#) for OPEN access instructions) the treating institution's identity is provided in order to ensure that the current (within 365 days) date of institutional review board approval for this study has been entered in the system.

6.0 STRATIFICATION FACTORS

Patient randomization will be dynamically balanced according to the following stratification factors: baseline pain score (BPI-SF item #4) (4-6 vs 7-10); and prior taxane use (yes vs. no).

7.1 Treatment

Agent	Dose	Schedule
Blinded drug (duloxetine 30 mg or placebo)	1 capsule PO Daily	Days 1-7
Blinded drug (duloxetine 30 mg or placebo)	2 capsules PO Daily	Days 8-84
Blinded drug (duloxetine 30 mg or placebo)	1 capsule PO Daily	Days 85-91

7.2 Study Plan

a. Initial Visit

Before beginning the intervention, patients will have a general physical exam (including recording of weight and height) and a mandatory blood draw for whole blood and serum (see [Section 15.1](#)). The patient will complete the **S1202** Brief Pain Inventory–Short Form (BPI-SF) prior to registration to confirm eligibility (see [Section 5.2d](#)). Patients will complete the following questionnaires prior to beginning treatment with blinded study drug:

S1202 Western Ontario and McMaster Universities Osteoarthritis (WOMAC) Index (Version 3.1)

S1202 Modified-Score for the Assessment and Quantification of Chronic Rheumatoid Affections of the Hands (M-SACRAH)

S1202 FACT – ES Trial Outcome Index (Version 4)

S1202 Patient Health Questionnaire-9 (PHQ-9)

It should take the patient about 20-25 minutes to complete the questionnaires. See [Section 15.2](#) for instructions for administration of the questionnaires.

The nurse or CRA must complete the **S1202** Cover Sheet for Patient-Completed Questionnaires.

Bottle #1 and #2 are dispensed at this visit. Patients will take 1 capsule daily for the first 7 days, then increase the dose to 2 capsules daily. The dose that should be taken each day should be listed on the patient calendar (see [Section 15.2c.1](#)).

b. Follow-up Visits

Follow-up visits will occur on Day 15, 43, 85, and 169 after start of treatment. Drug adherence will be ascertained by the nurse or CRA by review of the patient completed **S1202** Intake Calendar on Day 15, 43, and 85, as well as count of blinded drug capsules on the Day 43 and 85 visits. After the Day 85 pill count, the nurse or CRA must dispense bottle #3 to the patient to complete the Day 85 to Day 91 taper. Counts of blinded drug capsules remaining should be recorded on the **S1202** Treatment Form and the patient's medical record through the Day 85 visit. Adherence to AI should be recorded on the **S1202** Treatment Form at every visit. Adverse events will be assessed and recorded on the **S1202** Adverse Event Summary Form through the Day 85 visit. Use of pain medications, steroids, physical therapy, and acupuncture will be recorded on the **S1202** Supplemental Agents Reporting Form.

The nurse or CRA will contact the patient by telephone on Day 99 to assess adverse events following study drug discontinuation. Adverse events will be recorded on the **S1202** Adverse Event Summary Form

Patients will be instructed to complete the following questionnaires at the Day 15, 43, 85, and 169 visits. It takes about 20-25 minutes to complete the questionnaires.

S1202 Brief Pain Inventory Short Form (BPI-SF)

S1202 Western Ontario and McMaster Universities Osteoarthritis (WOMAC) Index (Version 3.1)

S1202 Modified-Score for the Assessment and Quantification of Chronic Rheumatoid Affections of the Hands (M-SACRAH)

S1202 FACT – ES Trial Outcome Index (Version 4)

S1202 Global Ratings of Change in Joint Pain and Stiffness

Patients will also be instructed to complete the following self-administered questionnaire at the Day 43 and 85 visits. It takes about 5-10 minutes to complete the assessment.

S1202 Patient Health Questionnaire-9 (PHQ-9).

The nurse or CRA will also complete the **S1202** Cover Sheet for Patient-Completed Questionnaires at each visit to indicate whether or not the patient completed the questionnaires, if the patient required assistance and the method for completing the questionnaires. If one or more of the questionnaires was not completed, an overall reason must be indicated on the Cover Sheet. See [Section 15.2](#) for detailed instructions for administration of the questionnaires.

Additionally, at the Day 85 visit, blood will be drawn for serum biomarkers (see [Section 15.1](#)).

All patients must taper off study drug after the Day 85 visit by decreasing the dose to 1 capsule daily for 7 days. After completing the taper of the study drug, if a patient wishes to take commercially-available duloxetine, she should take at least 7 days of duloxetine 30 mg daily prior to increasing the dose to 60 mg daily, in order to minimize the chance of developing side effects. She is permitted to start this at any time following completion of the taper of the study drug (Day 92).

7.3 Drug Compliance Documentation

Drug compliance will be recorded by patients in the Intake Calendar (see [Appendix 18.2](#)). Institutional CRAs will review and ascertain patient adherence with protocol therapy at the end of treatment for each visit. Calendar should be kept in the patient's clinic chart. Note that the Intake Calendar is provided only as a tool for tracking patient compliance. Sites may utilize institutional pill diaries or other source documentation in place of the Intake Calendar at the discretion of the treating physician.

7.4 Criteria for Discontinuation from Protocol Intervention

- a. Evidence of new cancer (except for basal squamous skin cancer or in situ cervical cancer) or cancer recurrence at any time.*
- b. Unacceptable toxicity.*
- c. Delay of study drug for any reason > 28 days.
- d. Completion of 13 weeks of treatment.
- e. Discontinuation of AI therapy or change to a different aromatase inhibitor medication during protocol treatment.* (Note: a delay of 28 days or more will be considered discontinuation of AI therapy.)
- f. The patient may withdraw from the study at any time for any reason.*

* If a patient is taking 2 capsules of blinded study drug daily and discontinues therapy prior to the Day 85 visit, she should decrease the dose to 1 capsule daily for 7 days prior to permanently stopping the blinded study drug. If a patient goes off protocol intervention for any reason before the Day 85 visit, the **S1202** Supplemental Agents Reporting Form and the patient questionnaires required at each subsequent visit should continue to be administered according to the protocol assessment schedule. See [Section 14.4i](#) for off protocol intervention data submission requirements.

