8.2 General Considerations

Patients who are taking narcotics, tramadol, gabapentin, and/or pregabalin at study registration should continue to take a stable dose of medication or should decrease their dose during study participation, as tolerated. Dose increases for these medications should be discouraged.

Patients who need additional analgesic medication during study participation are requested to take acetaminophen. Patients should not undergo therapy with other treatment modalities such as physical therapy, acupuncture, systemic steroids, or intra-articular steroid injections during study participation unless medically necessary. Usage of all medications and other therapies for treatment of pain should be documented on the **S1202** Supplemental Agents Reporting Form.

Caution should be taken if patients take aspirin or non-steroidal anti-inflammatory drugs during study participation because of the increased risk of bleeding when these medications are used in combination with duloxetine.

Caution should be taken if patients take triptan medications, tramadol, linezolid, or other serotonergic medications during study participation because of the increased risk of serotonin syndrome when these medications are used in combination with duloxetine.

Duloxetine has been associated with an increased risk of suicide. Therefore, at the day 43 and 85 study visits, the answer to question #9 on the PHQ-9 should be reviewed before the patient leaves the clinic. In addition, all patients should be asked about suicidal thoughts or actions at the Day 15 study visit and Day 99 telephone call. If a patient reports suicidal thoughts or actions, or answers anything other than "Not at all" to question #9, the treating physician should be immediately notified.

NOTE: Concomitant therapy with heparin and warfarin is not permitted while on study treatment.

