8.3 Dose Modifications

Grade 1 and Grade 2 Toxicity

If Grade 1 or 2 toxicities occur that are felt to be possibly, probably, or definitely related to study drug, monitor as needed until problem has resolved (i.e., Grade 0), stabilized (i.e., remains as Grade 1 or Grade 2), or is otherwise explained. If Grade 1 or Grade 2 symptoms persist, the local SWOG investigator will assess whether symptom management should be initiated, or whether the dose should be reduced from 2 capsules per day to 1 capsule per day. If Grade 1 or 2 symptoms persist while taking 1 capsule per day, the local SWOG investigator will assess whether symptom management should be initiated (if that has not already been done), or whether the patient should be removed from protocol treatment. No dose re-escalations are allowed. Follow-up will be conducted at the intervals specified in the protocol.

Grade 3 or Grade 4 Toxicity

If a patient develops any Grade 3 toxicity possibly, probably, or definitely related to the study drug, the patient should decrease the dose to 1 capsule daily for 7 days (if deemed medically safe to do so). If the symptoms resolve to Grade 0-2, the dose should be continued at 1 capsule per day. This dose may be maintained if Grade 3 toxicity does not recur. If at the 1 capsule a day dose the participant is still experiencing problems, she can be given a 1 week drug holiday from the blinded study drug. Subsequently, the patient may be re-challenged at the 1 capsule per day dose. Follow-up will continue at the intervals specified in the protocol. If symptoms do not recur (i.e., if symptoms resolve to Grade 0), the dose should be maintained, and no dose re-escalations are allowed. If Grade 3 drug-related toxicity does not improve to a Grade 0, 1, or 2 level within 1 week at the reduced dose, the patient should be removed from all protocol treatment. If the patient develops any Grade 4 toxicity possibly, probably, or definitely related to the study drug, the patient should decrease the dose to 1 capsule daily for 7 days (if deemed medically safe to do so) and then be removed from protocol treatment. Patient will also be removed from protocol treatment if there is a delay of study intervention >28 days.

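### Sections 7.4 and 8.3 give different step-down instructions for a patient on 2 capsules who stops early for severe drug-related toxicity

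*Combined protocol and SAP*

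**What the plan says.** Section 7.4 gives six reasons for leaving protocol intervention. Four carry an asterisk: new or recurrent cancer, unacceptable toxicity, stopping or changing the AI, and patient withdrawal. The asterisk leads to a footnote whose trigger is "If a patient is taking 2 capsules of blinded study drug daily and discontinues therapy prior to the Day 85 visit". Its instruction is that "she should decrease the dose to 1 capsule daily for 7 days prior to permanently stopping the blinded study drug". The footnote states no exception and does not mention Section 8.3.

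Section 8.3 deals with drug-related toxicity by grade. The Grade 4 rule opens "If the patient develops any Grade 4 toxicity possibly, probably, or definitely related to the study drug" and tells the patient to go to "1 capsule daily for 7 days (if deemed medically safe to do so) and then be removed from protocol treatment". For drug-related Grade 3 toxicity the same step to 1 capsule for 7 days appears with the same safety proviso. There it is a dose reduction, with removal only if the toxicity does not improve within a week at the lower dose.

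Both sections say should, not must. Neither says which prevails. Section 8.3 does not say what to do when the step-down is not safe.

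**The concern.** Section 7.4 is where a site looks when it takes a patient off treatment, and toxicity is one of its named reasons. A site that follows its footnote as written steps the patient down for a week whatever the clinical judgement on safety. A site that follows Section 8.3 makes that judgement first. The proviso appears twice in 8.3, so its absence from 7.4 looks like an omission rather than a decision.

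At stake is whether a patient with a severe reaction attributed to the study drug is given more of it on the strength of the protocol's own wording. Treatment is blinded, so a site would apply either instruction without knowing what the capsules contain.

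**Working it through.** The plan states no figure on this point, so there is nothing to recompute. The check is a comparison of the two texts.

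**Step 1: whom the footnote reaches.** Section 7.1 gives 1 capsule on Days 1-7 and 2 capsules on Days 8-84. The footnote applies only to a patient on 2 capsules who stops before the Day 85 visit. It therefore reaches patients from Day 8 on who have not already been reduced.

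**Step 2: each kind of early stop under both sections.**

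| Situation | Section 7.4 footnote | Section 8.3 | Conflict? |
|---|---|---|---|
| Grade 1-2, drug-related | Condition not met once she is on 1 capsule | Removal considered when symptoms persist on 1 capsule | No |
| Grade 3, drug-related, reduction judged safe | Condition not met, since she is already on 1 capsule when removed | Reduce; remove if no improvement within 1 week | No |
| Grade 3, drug-related, reduction judged unsafe, patient stops | Step down for 7 days | Proviso not met; no alternative stated | **Yes** |
| Grade 4, drug-related, step-down judged safe | Step down for 7 days | Step down for 7 days, then remove | No |
| Grade 4, drug-related, step-down judged unsafe | Step down for 7 days | Proviso not met; no alternative stated | **Yes** |
| Cancer, AI change, withdrawal | Step down for 7 days | Not covered | No |
| "Delay of study drug for any reason > 28 days" | No asterisk | Remove; no step-down mentioned | No |

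**Step 3: what differs.** In the two conflicting rows the footnote calls for 1 capsule × 7 days = 7 capsules, while the proviso in 8.3 exempts the patient from that step.

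**Step 4: does another section settle it?** Section 7.2b requires a taper after the Day 85 visit, but that concerns scheduled completion. Section 8.2 does not discuss how to stop. No section reviewed sets an order of precedence.

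**Step 5: effect on the analysis.** The sample size in Section 11.1 uses no input that depends on the step-down. Section 7.4 keeps the questionnaires on schedule after a patient leaves intervention, and Section 11.1 analyses all eligible randomized patients.

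**The case against.** The strongest reply is that the sections can be read together. The 7.4 footnote is a general default, 8.3 is the specific rule for drug-related Grade 3 and 4 toxicity, and the specific qualifies the general. Both say should, which leaves room for judgement, and most clinicians would use it. This is a fair account of what was probably intended, and it limits the seriousness. It does not remove the conflict: 7.4 is itself specific to toxicity through its second criterion, it does not point to 8.3, and no section reviewed ranks the two.

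The objection also stands on scope. A reader might infer that the sections disagree on every early stop from 2 capsules. They do not, because 8.3 is silent on stops for cancer, AI change or withdrawal. A reader might also infer that 8.3 tells the site to stop the drug at once when the step-down is unsafe. It does not say so; that is an inference from the proviso.

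A reader might extend the point to a patient who stops because she needs an anticoagulant, since 8.2 says "Concomitant therapy with heparin and warfarin is not permitted while on study treatment". But needing one is not a listed 7.4 criterion, 8.3 does not mention it, and the prohibition would itself cover step-down days. It is not part of this conflict.

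**Conclusion.** The point holds in a narrow form. Sections 7.4 and 8.3 differ for a patient on 2 capsules who stops before Day 85 because of drug-related Grade 4 toxicity, or Grade 3 toxicity where even the reduction is judged unsafe, whenever the step-down is not considered safe. The difference is up to 7 capsules per affected patient. It is an internal inconsistency in a safety instruction and should be corrected. It is not a flaw in the design or the analysis.

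The number affected is small, but the documents give no usable rate. A reader might take the pilot's 7 of 34 (20.6%) adverse-event stops from Section 2.0 as the base rate. That does not fit. Most of those stops came within a few days of starting, when the pilot dose was 30 mg daily; patients stopping that early here would still be on 1 capsule, outside the footnote. The reasons given included Grade 1-2 symptoms, and the only Grade 3 or 4 event was thought unlikely to be related.

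A reader might also infer that exposure and adverse-event attribution are distorted in the duloxetine arm only. The documents do not show this. Attribution is made blind in both arms, and the 30-day expedited reporting window in Section 16.1 runs from the last administration in either arm.

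The conclusion assumes that no text between Sections 8.3 and 8.5, which was not available for this review, sets the precedence.

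**What to change.** The sponsor should reconcile the 7.4 footnote with Section 8.3 so that one statement governs early stopping for toxicity, and 7.4 should cross-refer to it. That statement should also cover the case 8.3 leaves open, where the step-down is not judged safe. What it says is for the clinical team to decide; this review takes no view on which instruction is right.

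The cost is about one sentence in 7.4, with a matching clarification in 8.3, made by amendment. It needs no added patients, visits or procedures and no change to the sample size or the analysis.
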